3.4.2.2. Adjusted Outcomes Analyses

To examine the associations between treatment group (prasugrel versus clopidogrel) and dependent categorical resource use outcomes (for example, rehospitalizations for CV events), hazard ratios will be calculated using Cox proportional hazards regression. Models will be constructed as described previously in Section 3.4.1.

For analyses of costs, length of stay, and other continuous economic outcomes, IPW will be used. Each patient who received prasugrel or clopidogrel will be weighted by the inverse of the probability of receiving prasugrel. The propensity score and inverse probability weights will be derived as described previously in Section 3.4.1.

Due to the unknown distribution of continuous economic outcomes and the skewness of the data (especially direct and indirect costs), the comparison of continuous outcomes between cohorts will be conducted using non-parametric bootstrapping on IPW adjusted differences in means costs. A 95% confidence interval for the IPW-adjusted cost in both groups and difference in mean costs between the groups will be obtained based on percentiles of the bootstrap distribution. The primary independent variable will be treatment cohort (prasugrel versus clopidogrel) and other independent variables (covariates) will include baseline demographic and clinical characteristics, and baseline treatment utilization.

Differences in healthcare resource utilization and related costs between patients treated with prasugrel versus clopidogrel will be assessed for 1) the ACS-PCI subgroup with no prior stroke or TIA (primary economic outcomes analysis population) and 2) the overall ACS-PCI population (economic outcomes analysis subgroup), and additional subgroups may be considered. As a separate sensitivity analysis, a Generalized Linear Model (with gamma specification and log link function) will be used to model costs between treatment groups. The primary independent variable will be treatment cohort (prasugrel versus clopidogrel) and other independent variables (covariates) will include baseline demographic and clinical characteristics, and baseline treatment utilization.

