3.3. Research Design

3.3.1. Study Design

Study B020 is designed as a retrospective cohort study evaluating data for patients presenting with ACS managed with a PCI from 6 to 12 academic centers in the US from 01 January 2010 to 30 June 2013, with any follow-up data available for analysis. This study will evaluate the comparative effectiveness and economics of prasugrel relative to clopidogrel in approximately 8,600 patients (minimum 4,300 receiving prasugrel) in a usual care environment from academic centers in the US. These academic centers maintain institutional databases related to baseline characteristics, procedural characteristics and clinical and economic outcomes during and following index hospitalization of patients with ACS undergoing PCI.

The participating academic centers will run a query in their ACS-PCI database to identify all patients who received prasugrel or clopidogrel between 01 January 2010 and 30 June 2013. The study period was selected based on the approval and steady availability of prasugrel in the US market at the end of 2009 and by the need for a study with a minimum 90-day follow-up in this population. The primary endpoint of the study will be at 90 days from index hospital admission; at this point in therapy, the adherence rate is expected to continue to be high while the switching rate is expected to be low ($\leq 10\%$).

Figure 1 illustrates the study time periods.

Abbreviations: ACS = acute coronary syndromes; PCI = percutaneous coronary intervention.

Figure 1. Study B020 design for patients with ACS managed with PCI and treated with prasugrel or clopidogrel between 01 January 2010 and 30 June 2013.

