Total follow-up for each patient in Study B020 will be defined as time until death, last follow-up or 365 days following hospital admission for the index PCI, whichever comes first. To evaluate the associations between treatment group (prasugrel versus clopidogrel) and dependent outcomes, hazard ratios will be calculated using Cox proportional hazards regression. Median event free survival time will also be reported. In addition to age, gender and race, any baseline demographic, clinical, or procedural characteristic demonstrating a significant ($p < 0.1$) difference between groups will be included in the multivariable model. The model will also include other covariates that might be pertinent to the clinical outcome even if there are no significant differences in this cohort (for example, diabetes mellitus [DM], smoking status, etc.). Using these candidate covariates, a final multivariate model will be generated using a stepwise selection procedure to ensure model parsimony. The primary exposure of interest (prasugrel versus clopidogrel) will be forced in this final model.

As a separate sensitivity analysis, IPW will be used to adjust the selection bias for the treatment allocation. The propensity score will be generated using a non-parsimonious logistic regression model with the dependent variable as prasugrel versus clopidogrel treatment. From this model, each patient will be ascribed a predicted probability that reflects the propensity to have received prasugrel or clopidogrel at discharge. Inverse probability weights will be derived for all observations using the propensity scores, and then regression analyses will be repeated using these weights.

The primary analysis will include the overall ACS/PCI population. All analyses will be repeated in the all subgroups listed in Section 3.3.3.

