3.4.3. Bias Adjustment

Based on prior studies (Bae et al. 2012; Wang et al. 2013), significant differences in baseline and other characteristics between groups are expected. Therefore, 2 types of statistical procedures will be performed to account for such bias; these include multivariate and inverse propensity weighting.

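### Protocol 3.4.2.2 gives clopidogrel patients the same weight, 1/PS, as prasugrel patients, so the weighting as written does not remove confounding from adjusted costs and length of stay

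*Protocol*

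**What the plan says.** Protocol 3.4.2.2 makes weighting the main adjustment for continuous economic outcomes: "For analyses of costs, length of stay, and other continuous economic outcomes, IPW will be used". It then gives the rule: "Each patient who received prasugrel or clopidogrel will be weighted by the inverse of the probability of receiving prasugrel". The next sentence refers back: "The propensity score and inverse probability weights will be derived as described previously in Section 3.4.1".

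Protocol 3.4.1 fits a logistic model for prasugrel versus clopidogrel, from which "each patient will be ascribed a predicted probability that reflects the propensity to have received prasugrel or clopidogrel at discharge". On the weights it says only: "Inverse probability weights will be derived for all observations using the propensity scores, and then regression analyses will be repeated using these weights". It gives no formula by arm.

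Inference on the weighted contrast is by bootstrap: "the comparison of continuous outcomes between cohorts will be conducted using non-parametric bootstrapping on IPW adjusted differences in means costs". A gamma GLM with log link is the sensitivity analysis for costs.

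The SAP does not settle the weights. Item 4 of the sensitivity analyses in SAP 6.1 describes IPW for MACE in equally general terms. SAP 6.2.1 and 6.2.2 are headings whose content is deferred to Addendum 1. SAP 7.1 describes DRG costing and a bootstrap interval for mean hospital costs, but no weights.

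**The concern.** To compare two treatments, each patient is weighted by the inverse probability of the treatment that patient actually received. The rule in 3.4.2.2 names both arms and gives both the inverse probability of prasugrel. A clopidogrel patient who was very unlikely to get prasugrel then receives a very large weight, where the conventional weight would be close to 1.

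The protocol itself anticipates confounding: "significant differences in baseline and other characteristics between groups are expected" (3.4.3). The affected analysis is the main adjusted comparison for these outcomes. The economic objective has its own hypothesis (3.2.3) and a planned manuscript (3.8). A percentile bootstrap that uses the same weights would put its interval around the same confounded difference, so it would give no warning.

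**Working it through.** The plan attaches no figure to the weighting rule, so there is none to reproduce. The check is algebraic, then numerical.

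**Inputs**
- Rule as written: w = 1/e(X) in both arms, with e(X) = P(prasugrel | X) (Protocol 3.4.2.2).
- Prasugrel share π: Protocol 3.3.1 plans about 8,600 patients with at least 4,300 on prasugrel, and 4,300/8,600 = 0.50. Shares of 0.30 and 0.70 are also shown.
- Covariate distributions: not in the documents. Assumed here: a normal covariate with equal SD in both arms and a raw standardised difference of 0.2 to 0.8, and binary covariates with various prevalences.

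**Step 1: algebra.** Let f1 and f0 be the covariate densities on prasugrel and clopidogrel, and f = πf1 + (1 − π)f0 the whole cohort. Then e = πf1/f and 1 − e = (1 − π)f0/f.
- Prasugrel, weight 1/e: f1/e = f/π, which is the whole-cohort distribution.
- Clopidogrel, conventional weight 1/(1 − e): f0/(1 − e) = f/(1 − π), also the whole-cohort distribution. The arms match.
- Clopidogrel, weight as written 1/e: f0/e is proportional to f(1 − e)/e. This is the whole cohort tilted toward patients unlikely to get prasugrel.

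Under the written rule the ratio of the weighted arm densities is proportional to e/(1 − e), hence to f1/f0, as in the raw data. The arms cannot match unless e is constant, that is, unless there was no confounding by X to begin with.

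**Step 2: binary covariate, 2% prasugrel versus 10% clopidogrel, π = 0.5.**
- e(1) = 0.02/0.12 = 0.1667, so 1/e = 6. e(0) = 0.98/1.88 = 0.5213, so 1/e = 1.918.
- Prasugrel: 0.02 × 6 = 0.12 and 0.98 × 1.918 = 1.88. Weighted prevalence 0.12/2.00 = 0.060.
- Clopidogrel as written: 0.10 × 6 = 0.60 and 0.90 × 1.918 = 1.727. Weighted prevalence 0.60/2.327 = 0.258.
- Difference −0.198, against −0.080 crude (ratio 2.47).
- Clopidogrel with 1/(1 − e): 0.10 × 1.2 = 0.12 and 0.90 × 2.089 = 1.88. Weighted prevalence 0.060, difference 0.

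**Step 3: binary covariate, 40% versus 60%, π = 0.5.**
- e(1) = 0.4 and e(0) = 0.6, so the weights are 2.5 and 1.667.
- Prasugrel: 1.0/(1.0 + 1.0) = 0.500. Clopidogrel as written: 1.5/(1.5 + 0.667) = 0.692.
- Difference −0.192, against −0.200 crude. With 1/(1 − e) the clopidogrel value is 0.500 and the difference is 0.

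**Step 4: normal covariate, raw difference d, π = 0.5.** The prasugrel arm has weighted mean d/2. The clopidogrel arm has weight proportional to f0 + f0²/f1, with mean −d·exp(d²)/(1 + exp(d²)). The difference is d/2 + d·exp(d²)/(1 + exp(d²)). For d = 0.50: 0.250 + 0.50 × 1.284/2.284 = 0.531.

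**Results at π = 0.5** (normal rows in units of the raw SD)

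| Covariate (prasugrel vs clopidogrel) | Crude | 1/PS in both arms | 1/PS and 1/(1 − PS) |
|---|---|---|---|
| Normal, d = 0.20 | 0.200 | 0.202 | 0.000 |
| Normal, d = 0.50 | 0.500 | 0.531 | 0.000 |
| Normal, d = 0.80 | 0.800 | 0.924 | 0.000 |
| Binary, 2% vs 10% | −0.080 | −0.198 | 0.000 |
| Binary, 5% vs 10% | −0.050 | −0.071 | 0.000 |
| Binary, 40% vs 60% | −0.200 | −0.192 | 0.000 |
| Binary, 30% vs 70% | −0.400 | −0.345 | 0.000 |
| Binary, 10% vs 5% | 0.050 | 0.038 | 0.000 |

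**Step 5: other prasugrel shares (0.30; 0.70).** Normal d = 0.50: 0.525; 0.527. Binary 2% vs 10%: −0.233; −0.156. Binary 40% vs 60%: −0.185; −0.197. Over a grid of binary prevalences from 2% to 98%, the written rule left a larger gap than crude in 29%, 33% and 38% of pairs at shares of 0.30, 0.50 and 0.70. This is a count over a grid, not a probability for this cohort.

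If cost is linear in the covariate, the bias in the cost difference is the cost coefficient times the remaining imbalance. The last two columns of the table therefore carry over proportionally.

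**The case against.** The strongest defence is that the sentence is a drafting slip. The sentence after it sends the reader to 3.4.1, whose wording about receiving either drug is compatible with conventional weights, and the stated purpose is to adjust for baseline differences. A programmer following 3.4.1 might well use 1/(1 − PS) for clopidogrel, and Addendum 1 may give that formula. This stands as a reason not to assume that the wrong weights would be used. It does not remove the point, because 3.4.1 never states the clopidogrel weight and the only explicit rule is the faulty one.

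A second defence is the gamma GLM, which adjusts by covariates and does not use the weights. A disagreement with the weighted cost result could expose the problem. This stands for costs. For length of stay the cover is less clear: Protocol 3.4.2.2 describes the GLM for costs only, although the table listing in SAP 12 names it for continuous economic variables.

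Three stronger readings are tempting, and the documents support none of them:
- *The rule is always worse than no adjustment.* That holds for the normal covariates in the table, but not for several of the binary ones. Many listed baseline fields are 0/1, and no distributions are given.
- *The error favours prasugrel.* That requires costlier patients to be channelled to clopidogrel. Protocol 3.4.3 expects differences between groups but gives no direction for cost.
- *Event or rehospitalisation comparisons are distorted too.* Categorical resource use is analysed by Cox regression under 3.4.2.2, outside this sentence. Protocol 3.4.1 and SAP 6.1 do not contain the faulty rule.

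**Conclusion.** The rule is wrong as written. That it fails to remove confounding follows from the algebra and needs no assumption about the covariates beyond their being related to treatment. How much imbalance remains does depend on assumptions. At equal arms it ranges in the cases shown from about 2.5 times the crude gap (2% versus 10%) to somewhat below it (10% versus 5%: 0.038 against 0.050), while conventional weights give zero in every case. The fair statement is that confounding is not removed and may be made larger.

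The reach is limited to adjusted costs, length of stay and other continuous economic measures, all secondary. The primary 90-day MACE analysis is untouched. Whether the error would reach the results depends on Addendum 1 and on the programming, neither of which can be seen. Because this is the main adjustment for those outcomes and no supplied text corrects it, it should be put right before the economic analysis is run.

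**What to change.** Replace the sentence in Protocol 3.4.2.2 with: *Prasugrel patients will be weighted by 1/PS and clopidogrel patients by 1/(1 − PS), where PS is the estimated probability of receiving prasugrel.* State the same formula in Addendum 1, and report covariate balance after weighting, which would reveal this kind of error directly.

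Stabilising the weights and re-estimating the PS in each bootstrap sample are reasonable options, but neither is needed to correct the error. The cost is one sentence in each document and one balance table. No new data are required.

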3.4.3. Bias Adjustment

Based on prior studies (Bae et al. 2012; Wang et al. 2013), significant differences in baseline and other characteristics between groups are expected. Therefore, 2 types of statistical procedures will be performed to account for such bias; these include multivariate and inverse propensity weighting.

3.4.4. Subgroups

Associations for the primary MACE outcome will be examined in the pre-defined clinical subgroups of interest as described in Section 3.3.3. Stratum-specific hazard ratios will be calculated within each subgroup using Cox proportional hazards regression. Formal interaction testing will be performed between the main effects of subgroup (yes/no) and treatment allocation (prasugrel versus clopidogrel) on the MACE endpoint. Interaction terms with p-value <0.05 will be considered significant.

3.4.5. Multiplicity

The primary endpoint of interest in the present study is 90-day MACE, for which a Type I error rate of 0.05 will be used. All other endpoints are secondary and therefore no multiplicity adjustments will be performed.

3.4.6. Missing Data

It is anticipated that the amount of missing data will be minimal in the present study as sites are specifically asked to ensure that the data elements being requested are available. In the instance that baseline clinical or procedural data are missing, data will be imputed with values using multiple imputations with the mi command in Stata. Missing outcome data will not be imputed.

3.4.7. Robustness

The primary analysis will involve multivariate Cox proportional hazards regression as described above. The analysis will incorporate a step-wise selection procedure to generate a parsimonious model with selected covariates. Several sensitivity analyses will be performed to ensure that the primary findings are robust. First, select covariates will be selected using different approaches (forward and backward selection) to assess whether or not the association for the primary variable of interest changes substantially. Second, all analyses will be repeated in an IPW-adjusted cohort.

These additional analyses are meant to be confirmatory (that is, yield approximately the same answer) to the primary analysis.

3.4.8. Sample Size and Power Considerations

Study B020 is designed to assess the difference in MACE associated with prasugrel versus clopidogrel in patients presenting with ACS managed with a PCI from academic centers in the US from 01 January 2010 to 30 June 2013. Data from the Premier study and from TRANSLATE-ACS have suggested that the MACE rate at 90 days will be approximately 8.0%. Using 8.0% as the control rate, it is expected that the relative reduction with prasugrel will be

20% lower than with clopidogrel (hazard ratio 0.80). To achieve 80% power with an alpha of 0.05, and factoring in a 10% patient drop-out, at least 4,303 patients on prasugrel and clopidogrel need to be enrolled, yielding a minimum enrollment of 8,606 patients. If it is necessary to extend the window of time beyond 30 June 2013 in order to enroll an adequate number of patients, no protocol amendment will be required.

3.4.9. Study Limitations

- Data on mortality is partially provided by the Social Security Death Index (SSDI) and data for patients with a mortality record in the SSDI may not be current.
- As the databases are based on a large convenience sample, a limitation of its interpretation is that the results may not be generalizable to other populations. As these centers are select centers providing tertiary care in most instances, the data may not be generalizable to overall care in the US.
- In this database, there are limited/no data that can address known treatment switches to another oral antiplatelet ([OAP]; for example, clopidogrel). Given data from another database (Wang et al. 2013), it is expected that switching during the 90-day window will be less than 15%. However, due to the ITT approach planned for Study B020, outcomes assessed beyond 90 days may be biased towards the null if moderate/high rates of medication switching and discontinuation should occur.
- Several potential unmeasured confounders such as medication adherence and persistence are not available for analysis.
- Data entry (coding) errors may exist at the site of care resulting in initial misclassification of patients or, subsequently, misclassification of patient outcome. Medicare derived costs for DRGs will be included in the cost analyses; these may not represent actual costs incurred by patients in the database.
- While the ITT approach (primary analysis strategy) will attribute outcomes to the index therapy, patients whose outcomes are unknown at time of switching or discontinuation will be censored as true outpatient treatment adherence, persistence, or appropriate drug use will be unknown. Implications of this censoring (that is, assuming that none of those censored patients experience the target outcome after discontinuation or switching) on event rates and study power are unknown.
- The databases used in this study are maintained at academic centers, which are frequently tertiary care centers. It is possible that the loss of patient follow-up may be underestimated as it may not be known to these centers if a patient has an event and is hospitalized at another center.

3.5. Management and Reporting of Adverse Events

During the course of retrospective observational research, information pertaining to adverse reactions (ARs) will not be discovered as the study does not involve identifiable patient data associated with a Lilly drug. The data in this study is only being analyzed in aggregate, study data sets do not include safety measures, and there will be no medical chart review or review of free text data fields. Patient level data from the database will not be transferred to Lilly and/or Daiichi Sankyo Incorporated (DSI).

3.6. Product Complaints

During the course of retrospective observational research, information pertaining to product complaints will not be discovered as the study does not involve identifiable patient data associated with a Lilly drug.

3.7. Ethical Review and Regulatory Considerations

Observational studies will be submitted to ethical review boards (ERBs) for approval whenever required by local law. Regulatory authorities will be notified and approval sought as required by local laws and regulations. Progress reports will be submitted to ERBs and regulatory authorities as required by local laws and regulations.

This study will be conducted in accordance with the ethical principles that have their origin in the Declaration of Helsinki and that are consistent with good clinical practices and applicable US laws and regulations, as appropriate.

Attachment 1. Data Fields and Descriptions/Definitions

Data Field Term	VALUE	Description/Definition
Patient ID	#####	Patient ID for terms of this dataset (assigned after data consolidation, deidentified)
Date of Index PCI	DDMMYYYY	Actual date of procedure
Date of admission	DDMMYYYY	Actual date of admission associated with index event
Date of discharge	DDMMYYYY	Actual date of discharge associated with index event
Date of birth	DDMMYYYY	Date patient was born
Weight (Kg)	## in kilograms	Indicate the patient's weight in kilograms
Gender	0=male, 1=female	Indicate patient's gender
Height (cm)	### in cms	Indicate patient's height in cm
Hispanic	0=no, 1=yes	Hispanic or Latino Ethnicity: A person of Cuban, Mexican, Puerto Rican, Cuban, South or Central American, or other Spanish culture or origin, regardless of race. The term, "Spanish origin," can be used in addition to "Hispanic or Latino."
Black/African American	0=no, 1=yes	Black/African American (Race): Having origins in any of the black racial groups of Africa. Terms such as "Haitian" or "Negro" can be used in addition to "Black or African American."
White	0=no, 1=yes	White (Race): Having origins in any of the original peoples of Europe, the Middle East, or North Africa
Diabetes at baseline	0=no, 1=yes	Indicate if the patient has a history of diabetes mellitus regardless of duration of disease or need for antidiabetic agents. Supporting Definitions: Diabetes Mellitus: Diabetes mellitus is diagnosed by a physician or can be defined as a fasting blood sugar greater than 7 mmol/l or 126 mg/dL. It does not include gestational diabetes.

Data Field Term	VALUE	Description/Definition
Insulin-requiring diabetes at baseline	0=no, 1=yes	
Indicate if patient currently using insulin (Y/N)
 
Target Value: The value on arrival at this facility
 
Selections: Supporting Definitions: (none) Note(s): Patients placed on a pre-procedure diabetic pathway of insulin drip after arrival but were not on insulin therapy (treated by diet or oral method) are not coded as insulin treatment. If a patient had a pancreatic transplant, code "other", since the insulin from the new pancreas is not exogenous insulin.

Hypertension	0=no, 1=yes	
Hypertension is defined by any one of the following:
 
 • History of hypertension diagnosed and treated with medication, diet and/or exercise • Prior documentation of blood pressure greater than 140 mm Hg systolic and/or 90 mm Hg diastolic for patients without diabetes or chronic kidney disease, or prior documentation of blood pressure greater than 130 mm Hg systolic and/or 80 mm Hg diastolic on at least two occasions for patients with diabetes or chronic kidney disease • Currently on pharmacologic therapy for treatment of hypertension.
Hypercholesterolemia	0=no, 1=yes	
Indicate if the patient has a history of dyslipidemia diagnosed and/or treated by a physician. Target Value: Any occurrence between birth and arrival at this facility
 
Dyslipidemia: National Cholesterol Education Program criteria include documentation of the following:
 
 A. Total cholesterol greater than 200 mg/dL (5.18 mmol/l); or B. Low-density lipoprotein (LDL) greater than or equal to 130 mg/dL (3.37 mmol/l); or, C. High-density lipoprotein (HDL) less than 40 mg/dL (1.04 mmol/l). 
For patients with known coronary artery disease, treatment is initiated if LDL is greater than 100 mg/dL (2.59mmol/l), and this would qualify as hypercholesterolemia

Serum creatinine	in mg/dl	Pre-procedure value

Data Field Term	VALUE	Description/Definition
Serum hemoglobin	in g/dl	Pre-procedure value
Troponin		Pre-procedure value
CK-MB baseline	ng/ml	Pre-procedure value
Peak serum creatinine	in mg/dl	highest value; leave missing if not drawn
Nadir hemoglobin	in g/dl	lowest within 72 hours;. leave missing if not drawn
Peak CK-MB	ng/ml	highest 6-24 hours; leave missing if not drawn
Peak Troponin		highest 6-24 hours; leave missing if not drawn
Smoking	0=no, 1=yes	Indicate if the patient has smoked cigarettes anytime during the year prior to arrival Coding Instructions: at your facility. Target Value: Any occurrence between 1 year prior to arrival at this facility and arrival at this facility
Family history of CAD	0=no, 1=yes	Family Hx Premature CAD Direct Relatives: Family history includes any direct blood relatives (parents, siblings, children) who have had any of the following diagnosed at age less than 55 years for male relatives or less than 65 years for female relatives: 
 A. Angina B. Acute myocardial infarction C. Sudden cardiac death without obvious cause D. Coronary artery bypass graft surgery E. Percutaneous coronary intervention
Previous MI	0=no, 1=yes	Indicate if the patient has had at least one documented previous myocardial Coding Instructions: infarction. Target Value: Any occurrence between birth and arrival at this facility. Note(s): Code 'No' if the patient's only MI occurred at the transferring facility. Admit Source (3010) must be "Transfer in from another acute care facility." MI: A myocardial infarction is evidenced by any of the following: 
 A. A rise and fall of cardiac biomarkers (preferably troponin) with at least one of the values in the abnormal range for that laboratory [typically above the 99th percentile of the upper reference

Data Field Term	VALUE	Description/Definition
		
limit (URL) for normal subjects] together with at least one of the following manifestations of myocardial ischemia:
 
 a. Ischemic symptoms b. ECG changes indicative of new ischemia (new ST-T changes, new left bundle branch block, or loss of R wave voltage). c. Development of pathological Q waves in 2 or more contiguous leads in the ECG (or equivalent findings for true posterior MI). d. Imaging evidence of new loss of viable myocardium or new regional wall motion abnormality. e. Documentation in the medical record of the diagnosis of acute myocardial infarction based on the cardiac biomarker pattern in the absence of any items enumerated in a-d due to conditions that may mask their appearance (for example, peri-operative infarct when the patient cannot report ischemic symptoms; baseline left bundle branch block or ventricular pacing). 
B. ECG changes associated with prior myocardial infarction can include the following (with or without prior symptoms):
 
 a. Any Q-wave in leads V2-V3 ≥ 0.02 seconds or QS complex in leads V2 and V3 b. Q-wave ≥ 0.03 seconds and ≥ 0.1 mV deep or QS complex in leads I, II, aVL, aVF, or V4-V6 in any two leads of a contiguous lead grouping (I, aVL, V6; V4-V6; II, III, and aVF). c. R-wave ≥ 0.04 seconds in V1-V2 and R/S ≥ 1 with a concordant positive T-wave in the absence of a conduction defect. 
C. Imaging evidence of a region with new loss of viable myocardium at rest in the absence of a non-ischemic cause. This can be manifest as:
 
 a. Echocardiographic, CT, MR,

Data Field Term	VALUE	Description/Definition
		
ventriculographic or nuclear imaging evidence of left ventricular thinning or scarring and failure to contract appropriately (i.e., hypokinesis, akinesis, or dyskinesis).
 
b. Fixed (non-reversible) perfusion defects on nuclear radioisotope imaging (for example, MIBI, thallium).
 
D. Medical records documentation of prior myocardial infarction.

Previous PCI	0=no, 1=yes	
Indicate if the patient had a previous percutaneous coronary intervention. Target Value: Any occurrence between birth and arrival at this facility Note(s): Timeframe does NOT include PCIs performed after arrival. PCI: Percutaneous coronary intervention (PCI) is the placement of an angioplasty guide wire, balloon, or other device (for example, stent, atherectomy, brachytherapy, or thrombectomy catheter) into a native coronary artery or coronary artery bypass graft for the purpose of mechanical coronary revascularization.

Previous CABG	0=no, 1=yes	
Indicate if the patient had a previous coronary artery bypass graft (CABG) surgery. Target Value: Any occurrence between birth and arrival at this facility Note(s): Timeframe does NOT include CABG performed after arrival.

Prior CHF	0=no, 1=yes	
Indicate if there is a previous history of heart failure. Target Value: Any occurrence between birth and arrival at this facility. Note(s): A previous hospital admission with principal diagnosis of heart failure is considered evidence of heart failure history. Heart failure is defined as physician documentation or report of any of the following clinical symptoms of heart failure described as unusual dyspnea on light exertion, recurrent dyspnea occurring in the supine position, fluid retention; or the description of rales, jugular venous distension, pulmonary edema on physical exam, or pulmonary edema on chest x-ray. A low ejection fraction alone, without clinical evidence of heart failure does not qualify as heart

Data Field Term	VALUE	Description/Definition
		failure.
Prior PAD	0=no, 1=yes	
Indicate if the patient has a history of peripheral arterial disease (PAD) (includes upper and lower extremity, renal, mesenteric, and abdominal aortic systems).
 
Supporting Definitions: PAD: Peripheral arterial disease can include:
 
 A. Claudication, either with exertion or at rest. B. Amputation for arterial vascular insufficiency. C. Vascular reconstruction, bypass surgery, or percutaneous intervention to the extremities (excluding dialysis fistulas and vein stripping). D. Documented aortic aneurysm with or without repair. E. Positive non-invasive test (for example, ankle brachial index ≤ 0.9); ultrasound, magnetic resonance, computed tomography, or angiographic imaging of $> 50\%$ diameter stenosis in any peripheral artery (for example, renal, subclavian, femoral, iliac). 
For purposes of the Registry, peripheral arterial disease excludes disease in the carotid and cerebrovascular arteries.

Data Field Term	VALUE	Description/Definition
Prior Cerebrovascular Disease	0=no, 1=yes	
Indicate if the patient has a history of cerebrovascular Coding Instructions: disease. Target Value: Any occurrence between birth and arrival at this facility Cerebrovascular Disease documented by any one of the following:
 
 A. Cerebrovascular Accident (CVA): Patient has a history of stroke, i.e., loss of neurological function with residual symptoms at least 24 hrs after onset, presumed to be from vascular etiology. B. Transient Ischemic Attack (TIA): Patient has a history of loss of neurological function that was abrupt in onset but with complete return of function within 24 hrs, presumed to be due to vascular etiology C. Non-invasive/invasive carotid test with > 79% occlusion. D. Previous carotid artery surgery/intervention for carotid artery stenosis. 
This does not include neurological disease processes such as metabolic and/or anoxic ischemic encephalopathy.

Left ventricular ejection fraction (%)	## %	
If only a range is reported, report the median of the range (i.e.50-55%, is reported as 53%). If only a descriptive value is reported (i.e.normal), enter the corresponding percentage value from the list below:
 
 Normal = 60% Good function = 50% Mildly reduced = 45% Fair function = 40% Moderately reduced = 30% Poor function = 25% Severely reduced = 20% 
The Left Ventricular Ejection Fraction can be assessed via invasive (i.e. LV gram) or non-invasive (i.e. Echo, MR, CT or Nuclear) testing. If an ejection fraction is not measured during this admission and prior to the PCI, and their clinical status has not changed, it is acceptable to code an ejection fraction

Data Field Term	VALUE	Description/Definition
		that was obtained prior to arrival. LVEF: The left ventricular ejection fraction is the percentage of the blood emptied from the left ventricle at the end of the contraction.
CAD Presentation	1=No sx/s/no angina; 2=unlikely ischemic; 3=stable angina; 4=Unstable Angina; 5=Non-ST-elevation myocardial infarction, 6=ST-elevation myocardial infarction	
Indicate the patient's coronary artery disease (CAD) presentation. Choose Coding Instructions: the worst status. Target Value: The highest value between 7 days prior to arrival and current procedure Selections. Note(s): If the patient presents with atypical symptoms of myocardial ischemia (i.e. only shortness of breath, upper abdominal pain, left arm pain, etc.) that is known and documented to be myocardial ischemia, and is considered to be an anginal equivalent, code the selection that fits their presentation. If these symptoms are not thought to be or have not been proven to be the anginal equivalent, code "Symptom unlikely to be ischemic." If this is a subsequent episode of care (within 7 days), do not code the CAD Presentation from the previous episode of care. For STEMI and NSTEMI, code the highest value within 1 week of the current procedure. If this is a repeat visit to the cath lab during the same episode of care, code the CAD presentation based on the patients clinical status prior to the subsequent procedure. Selection Text Definition
 
 1. No symptom, no angina: No symptoms, No angina 2. Symptom unlikely to be ischemic: Pain, pressure or discomfort in the chest, neck or arms NOT clearly exertional or NOT otherwise consistent with pain or discomfort of myocardial ischemic origin. This includes

Data Field Term	VALUE	Description/Definition
		
patients with non-cardiac pain (for example, pulmonary embolism, musculoskeletal, or esophageal discomfort), or cardiac pain not caused by myocardial ischemia (for example, acute pericarditis).
 
 3. Stable angina: Angina without a change in frequency or pattern for the 6 weeks prior to this cath lab visit. Angina is controlled by rest and/or oral or transcutaneous medications 4. Unstable angina: There are three principal presentations of unstable angina: 
 a. Rest angina (occurring at rest and prolonged, usually >20 minutes) b. New onset angina (within the past 2 months, of at least Canadian Cardiovascular Society Class III severity); or c. Increasing angina (previously diagnosed angina that has become distinctly more frequent, longer in duration, or increased by 1 or more Canadian Cardiovascular Society class to at least CCS III severity). 5. Non-STEMI: The patient was hospitalized for a non-ST elevation myocardial infarction (STEMI) as documented in the medical record. Non-STEMIs are characterized by the presence of both criteria: 
 a. Cardiac biomarkers (creatinine kinase-myocardial band, Troponin T or I) exceed the upper limit of normal according to the individual hospital's laboratory parameters with a clinical presentation which is consistent or suggestive of ischemia. ECG changes and/or ischemic symptoms may or may not be present. b. Absence of ECG changes diagnostic of a STEMI (see STEMI) 6. STEMI: The patient presented with a ST elevation myocardial infarction (STEMI) or its equivalent as documented in the medical

Data Field Term	VALUE	Description/Definition
		
record. STEMI are characterized by the presence of both criteria:
 
a) ECG evidence of STEMI: New or presumed new ST-segment elevation or new left bundle branch block not documented to be resolved within 20 minutes. ST-segment elevation is defined by new or presumed new sustained ST-segment elevation at the J-point in two contiguous electrocardiogram (ECG) leads with the cut-off points: ≥ 0.2 mV in men or ≥ 0.15 mV in women in leads V2-V3 and/or ≥ 0.1 mV in other leads and lasting greater than or equal to 20 minutes. If no exact ST-elevation measurement is recorded in the medical chart, physician's written documentation of ST-elevation or Q-waves is acceptable.
 
a. If only one ECG is performed, then the assumption that the ST elevation persisted at least the required 20 minutes is acceptable. Left bundle branch block (LBBB) refers to new or presumed new LBBB on the initial ECG.
 
b. Cardiac biomarkers (creatinine kinase-myocardial band, Troponin T or I) exceed the upper limit of normal according to the individual hospital's laboratory parameters a clinical presentation which is consistent or suggestive of ischemia.
 
c. Note: For purposes of the Registry, ST elevation in the posterior chest leads (V7 through V9), or ST depression that is maximal in V1-3, without ST-segment elevation in other leads, demonstrating posterobasal myocardial infarction, is considered a STEMI equivalent and qualifies the patient for reperfusion therapy.

Data Field Term	VALUE	Description/Definition
